3.7 Exploratory analysis

3.7.2 Spleen length by manual palpation

Frequency of patients who have palpable spleen measurement will be provided. Spleen measurement by manual palpation at week 24 will be compared to the week 1 day 1 measurement. Descriptive statistics will be provided for the spleen length and percent change from baseline over time by the redefined treatment groups (details can be found in RAP M7.1 section 1.2.1) and overall. The maximum likelihood estimate and 95% exact binomial confidence interval will be also provided for patient who has $\geq 50\%$ spleen length reduction by manual palpation.

Data will be summarized for the set of patients from the FAS who have a valid corresponding baseline assessment.

The percentage change in spleen length is defined as:

$\% \text{ Change} = (\text{Post-baseline spleen length} - \text{Baseline spleen length}) \times 100 / \text{Baseline spleen length}$.

3.8 Safety evaluation

The assessment of safety will be based mainly on the frequency of adverse events and on the number of laboratory values that fall outside of pre-determined ranges. Other safety data (e.g. electrocardiogram, vital signs) will be considered as appropriate.

All safety outputs will be provided by study phase, treatment and overall by using the safety set. The safety summary tables will include only assessments collected no later than 30 days after study treatment discontinuation. All safety assessments will be listed and those collected later than 30 days after study treatment discontinuation will be flagged.

Adverse events of special interest will be summarized according to [Section 3.8.1.5](#).

3.8.1 Adverse events data

3.8.1.1 Coding of AEs

AEs will be coded using the Medical dictionary for regulatory activities (MedDRA) terminology. The latest version of MedDRA prior to the database lock will be used for reporting.

3.8.1.2 Grading of AEs

AEs will be graded according to the Common Terminology Criteria for Adverse Events (CTCAE) version 4.03.

If CTCAE grading does not exist for an adverse event, grades 1 – 4 corresponding to the severity of mild, moderate, severe, and life-threatening will be used. CTCAE grade 5 (death) will not be used in this study; rather, this information will be collected on the “End of Treatment” eCRF pages. In addition, information related to the death of a patient while in the study or within the follow-up period specified in the protocol will be collected in “Death” CRF page.

3.8.1.3 General rules for AE Reporting

AE summaries will include all AEs starting on or after study day 1 (i.e. on or after the day of the first intake of study treatment) and starting no later than 30 days after the end of treatment. All AEs will be listed. AEs starting prior to study day 1 and AEs starting later than 30 days after the last treatment date will be flagged in the listings.

AEs will be summarized by dose level for the number and percentage of patients having at least one AE, in each primary system organ class and for each preferred term (using MedDRA coding). A subject with multiple occurrences of an AE will be counted only once in the corresponding AE category. Separate AE summaries will be presented by the maximum CTCAE grade. A patient with multiple CTCAE grades for an AE will be summarized under the maximum CTCAE grade recorded for the event.

In addition, a summary of serious and non-serious adverse events with number of occurrences will be produced (an occurrence is defined as >1 day between start and prior end date of record of same preferred term) as per EudraCT requirements.

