8.1.1 Definitions and reporting

An adverse event is defined as the appearance of (or worsening of any pre-existing) undesirable sign(s), symptom(s), or medical condition(s) that occur after patient’s signed informed consent has been obtained. Abnormal laboratory values or test results occurring after informed consent constitute adverse events only if they induce clinical signs or symptoms, are considered clinically significant, require therapy (e.g., hematologic abnormality that requires transfusion or hematological stem cell support), or require changes in study medication(s).

For patients who sign the ICF, all AEs will be captured in the AE eCRF from time of signature through 30 days after permanent study drug discontinuation. For patients who fail screening, only SAEs will be captured in the AE eCRF page.

Adverse events that begin or worsen after informed consent should be recorded in the Adverse Events eCRF. Conditions that were already present at the time of informed consent should be recorded in the Medical History page of the patient’s CRF. Adverse event monitoring should be continued for at least 30 days (or 5 half-lives, whichever is longer) following the last dose of study treatment. Adverse events (including lab abnormalities that constitute AEs) should be described using a diagnosis whenever possible, rather than individual underlying signs and symptoms. When a clear diagnosis cannot be identified, each sign or symptom should be reported as a separate Adverse Event.

Adverse events will be assessed according to the Common Terminology Criteria for Adverse Events (CTCAE) version 4.03. If CTCAE grading does not exist for an adverse event, the

severity of mild, moderate, severe, and life-threatening, corresponding to Grades 1 - 4, will be used. CTCAE Grade 5 (death) will not be used in this study; rather, information about deaths will be collected on the appropriate eCRF.

The occurrence of adverse events should be sought by non-directive questioning of the patient (subject) during the screening process after signing informed consent and at each visit during the study. Adverse events also may be detected when they are volunteered by the patient (subject) during the screening process or between visits, or through physical examination, laboratory test, or other assessments. As far as possible, each adverse event should be evaluated to determine:

1. The severity grade (CTCAE Grade 1-4)
2. Its duration (Start and end dates)

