3. Its relationship to the study treatment (Reasonable possibility that AE is related: No, Yes)
4. Action taken with respect to study or investigational treatment (none, dose adjusted, temporarily interrupted, permanently discontinued, unknown, not applicable)
5. Whether medication or therapy taken (no concomitant medication/non-drug therapy, concomitant medication/non-drug therapy)
6. Outcome (not recovered/not resolved, recovered/resolved, recovering/resolving, recovered/resolved with sequelae, fatal, unknown)
7. Whether it is serious, where a serious adverse event (SAE) is defined as in [Section 8.2.1](#).

All adverse events should be treated appropriately. If a concomitant medication or non-drug therapy is given, this action should be recorded on the Adverse Event CRF.

Once an adverse event is detected, it should be followed until its resolution or until it is judged to be permanent, and assessment should be made at each visit (or more frequently, if necessary) of any changes in severity, the suspected relationship to the study treatment, the interventions required to treat it, and the outcome.

Progression of malignancy (including fatal outcomes), if documented by use of appropriate method (for example, as per RECIST criteria for solid tumors or as per Cheson's guidelines for hematological malignancies), should not be reported as a serious adverse event.

Adverse events separate from the progression of malignancy (example, deep vein thrombosis at the time of progression or hemoptysis concurrent with finding of disease progression) will be reported as per usual guidelines used for such events with proper attribution regarding relatedness to the drug.

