10.5.1.1 Adverse events (AEs)

Summary tables for adverse events (AEs) have to include only AEs that started or worsened during the on-treatment period, i.e. the *treatment-emergent* AEs. On-treatment assessment is defined as any assessment reported in the time interval from the start date of study treatment to 30 days following the last date of study treatment. However, all safety data will be listed and data collected outside the on-treatment period will be flagged.

The incidence of treatment-emergent adverse events (new or worsening from baseline) will be summarized by system organ class and or preferred term, severity (based on CTCAE 4.03 grades), type of adverse event, relation to each treatment schedule and by study phase.

Deaths and serious adverse events will be listed by patient and tabulated by type of adverse event and each treatment schedule by study phase.

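### The SAP selects AEs for its summary tables by start date alone, while the protocol also requires AEs that worsened on treatment, so an AE that began in screening and then worsened can be left out

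*SAP*

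**What the plan says.** The protocol sets the rule for the tables in 10.5.1.1: "Summary tables for adverse events (AEs) have to include only AEs that started or worsened during the on-treatment period". The on-treatment period runs from the start of study treatment to 30 days after its last date. The same section repeats the rule for incidence: "The incidence of treatment-emergent adverse events (new or worsening from baseline) will be summarized by system organ class".

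SAP 3.8.1.3 uses a different rule: "AE summaries will include all AEs starting on or after study day 1", with an upper limit on the start date of 30 days after the end of treatment. The remaining events are listed only: "AEs starting prior to study day 1 and AEs starting later than 30 days after the last treatment date will be flagged".

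Two parts of Protocol 8.1.1 bear on which events are in the database. Collection begins at consent: "all AEs will be captured in the AE eCRF from time of signature through 30 days after permanent study drug discontinuation". Each AE is then followed at every visit, with assessment "of any changes in severity, the suspected relationship to the study treatment", among other items. The SAP introduction presents the document as describing the analysis that the protocol specifies and declares no departure on this point.

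**The concern.** The two rules agree for any AE that begins on treatment. They differ for an AE that begins after consent but before the first dose and then becomes worse on drug. The protocol counts that event as treatment-emergent and the SAP does not.

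Safety is a secondary objective of both phases. Protocol 10.5.1 and SAP 3.8 both say that it will be judged mainly on the frequency of AEs. SAP 3.8.1.5 names AEs of special interest that include fatigue, nausea or vomiting, muscle-related events and thrombocytopenia. Some of these are symptoms that no laboratory table would show. A rule that drops on-treatment worsening bears directly on the main evidence for this objective, and its effect has only one direction.

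**Working it through.** No sample size, power or error rate is involved, so the check is a comparison of the texts.

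**Step 1. The two selection rules.** Let A be the AEs that start in the on-treatment window, and B the AEs that worsen in that window.

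- Protocol 10.5.1.1 tabulates A or B.
- SAP 3.8.1.3 tabulates A.
- The difference is the set of AEs in B but not in A: those that started before Day 1 and worsened afterwards.

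The SAP set is contained in the protocol set. Relative to the protocol, the SAP rule can remove events but cannot add any.

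**Step 2. Is the worsening limb restored elsewhere in the SAP?** Section 2.1.7 defines on-treatment by the date of the assessment and does not mention worsening of an AE. Sections 3.8, 3.8.1.4 and 3.8.1.5 list outputs without a separate selection rule. None of them brings the missing events back.

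**Step 3. Can such events be in the database?** Yes. For treated patients, AEs are recorded from consent, and screening lasts up to 21 days before the first dose (Protocol 7.1.1; SAP 1.1).

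**Step 4. Does a worsened event keep its screening start date?** The documents do not settle this.

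- For one continuing record: Protocol 8.1.1 follows changes in severity of an AE once it is detected, and SAP 3.8.1.3 summarises a patient with several grades for one AE at the maximum grade.
- For several records: Protocol 8.1.1 includes worsening of a pre-existing condition in the definition of an AE. The EudraCT occurrence rule in SAP 3.8.1.3 compares the start of one record with the end of the previous record of the same preferred term, which suggests that contiguous records may exist.

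Under one record, the event is lost from the tables. Under a new dated record at each grade rise, the worsened record starts on treatment and the SAP rule counts it.

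**Step 5. What one missing patient would change.** This gives the weight of one patient and is not an estimate of how many are affected. The denominators are the 20 patients of Phase II Stage 1 (SAP 3.5.2.1.2), the 27 of Phase Ib expansion plus Stage 1 (SAP 3.5.2.1.3), and the 50 treated in all (Amendment 2 rationale).

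| Group | Change per missing patient |
|---|---|
| Stage 1 alone | 1/20 = 5.0 percentage points |
| Expansion plus Stage 1 | 1/27 = 3.7 percentage points |
| All treated | 1/50 = 2.0 percentage points |

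A patient drops out of a table row only if no other qualifying AE places them in that row. A patient who stays in the row may still have the maximum grade understated.

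**The case against.** The strongest reply is that the loss depends on a recording convention that neither document states. If a rise in grade opens a new eCRF record, the SAP rule already counts it and the two rules give the same tables. This stands as a limit on the consequence. It does not remove the conflict in wording, and the SAP should not depend on an unstated convention.

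A second reply is that many complaints of myelofibrosis predate consent. Protocol 8.1.1 sends those to medical history and records them as AEs when they worsen. If that first happens on treatment, the AE starts on treatment and is counted. This also stands, and it narrows the gap to AEs whose onset falls between consent and Day 1.

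A reader might infer that the affected events disappear from the report altogether. The documents do not support that:

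- All AEs remain in the listings, with a flag for early onset.
- Graded laboratory worsening appears in the baseline-to-worst shift tables, and grade 3 or 4 laboratory and CK values are listed (SAP 3.8.2.1).
- DLTs are summarised on the dose-determining set (SAP 3.5.1.2).
- Reductions, interruptions and permanent discontinuations are tabulated from dosing records (SAP 3.3.5).
- Deaths have their own eCRF page (SAP 3.8.1.2).

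These outputs do not replace AE incidence. They do not give the frequency of worsening fatigue, myalgia or nausea, or an event's seriousness or suspected relation to study drug.

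A reader might also infer that the rule affected the decision on Stage 2. The SAP records that Stage 2 will not be enrolled (1.1 and 3.5.2.1), so this wording can now affect only the study report.

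**Conclusion.** The inconsistency is real. SAP 3.8.1.3 applies a narrower rule than Protocol 10.5.1.1, without stated reason, and nothing else in the SAP restores the difference. The affected events are AEs that first arise in the window of up to 21 days between consent and Day 1, worsen in grade on treatment, and stay in one record with the original start date. They would be absent from the AE summary tables in 3.8.1.4 and 3.8.1.5 and appear only as flagged listing entries.

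The direction is certain: relative to the protocol rule, AE incidence can only be understated. The size is unknown, because the documents give no rate of screening-onset AEs. A reader might try to derive one from the 82.4% anemia and 69.8% thrombocytopenia that Protocol 1.4.2.2.1 reports for the INC424 pivotal studies. Those figures describe AEs observed in those studies and say nothing about onset in this trial's screening window, so no count of affected patients can be built on them.

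The conclusion that events would actually be lost rests on the single-record assumption. The finding that the two rules differ does not.

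**What to change.** Change SAP 3.8.1.3 to the protocol rule. Include AEs that start, or increase in CTCAE grade over the last pre-dose grade, from the first dose to 30 days after the last dose. Apply the rule to all tables in 3.8.1.4 and 3.8.1.5.

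State in the same section how the eCRF records a grade change, whether as a new dated record or as dated grades within one event. The flag can be derived only if grade changes carry dates. If they do not, the SAP should say so. If each rise already opens a new record, the corrected wording should leave the counts unchanged and simply confirms the practice.

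The protocol rule covers start and worsening only. Becoming serious without a rise in grade is not part of it, so adding that criterion would be a separate choice for the sponsor and should not be presented as restoring the protocol.

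The cost is a change of SAP wording and one derivation. AE counts may become slightly less favourable.

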3.8.1.4 AE summaries

The following AE summaries will be produced. Overall category will be included:

- Number (%) of patients who died, had AEs, had SAEs, discontinued, had concomitant medication or had a dose reduction or interruption, by treatment group
- AEs, regardless of study drug relationship by primary system organ class, preferred term, maximum CTC grade and treatment group
- AEs suspected to be related to the study drug by primary system organ class, preferred term, maximum CTC grade and treatment group
- Deaths by primary system organ class, preferred term and treatment group
- Serious adverse events (SAE), regardless of study drug relationship, by primary system organ class, preferred term, maximum CTC grade and treatment group
- AEs leading to study drug discontinuation, regardless of study drug relationship, by primary system organ class, preferred term, maximum CTC grade and treatment group
- AEs requiring dose adjustment or study-drug interruption, regardless of study drug relationship, by primary system organ class, preferred term, maximum CTC grade and treatment group
- AEs which are not serious adverse events, regardless of study drug relationship, by primary system organ class, preferred term and treatment group
- AEs, regardless of study drug relationship, by preferred term and treatment group
- On-treatment deaths and serious adverse events by primary system organ class, preferred term and treatment group

3.8.1.5 Adverse events of special interest

Specific groupings of AEs, referred as AEs of special interest, will be considered and the number of patients with at least one event in each grouping will be reported by the redefined study treatment. Such groups consist of AEs for which there is a specific clinical interest in connection with LDE225 or INC424 treatment (i.e. compound and class related risks linked to the drug structure, mechanism of action, formulation and mode of administration).

- Muscle-related events, including CK elevation

- Nausea and/or Vomiting
- Diarrhea
- Fatigue
- Dysgeusia
- Alopecia
- Weight decreased
- Decreased Appetite
- Thrombocytopenia

The classification and definition of AEs of special interest reflects the current version of the Safety Profiling Plan (SPP) and might be updated at the time of the data base lock for the analyses based on the latest approved version of the SPP.

The following summaries will be provided for the AEs of special interest:

- AEs of special interest, by group, preferred term and treatment group. This includes all CTC grades, suspected AEs to be related to study drug, SAEs, AEs requiring dose adjustment and AEs leading to discontinuation from study treatment.

3.8.2 Laboratory data

The summaries will include all laboratory assessments collected no later than 30 days after study treatment discontinuation. All laboratory assessments will be listed and those collected later than 30 days after study treatment discontinuation will be flagged in the listings.

The laboratory data will be classified into CTC grades according to the NCI Common Terminology Criteria for Adverse Events (CTCAE) v4.03. If value within normal limits is assigned grade 0 as well as assigned a non-zero grade by the NCI Toxicity Criteria, the severity will be assigned to grade 0. These values are not counted in the frequency distribution of the highest NCI toxicity grade even if the value met the criteria of a nonzero grade. This resolves cases where a laboratory value could simultaneously fall in the normal range and in the range of a non-zero grade under NCI toxicity Criteria.

3.8.2.1 Descriptive analyses

The following summaries will be produced for the hematology and biochemistry laboratory data (by laboratory parameter):

- Shift tables using CTC grades to compare baseline to the worst post-baseline value, by treatment and overall
- For laboratory parameters without CTC grade: shift tables using normal ranges to compare baseline to the worst post-baseline value, by treatment and overall

The following listings will be produced for laboratory data:

- Listing of laboratory data, with values flagged to show the corresponding CTC grades and the classifications relative to the laboratory reference ranges by treatment. This listing will be provided for hematology, biochemistry and urinalysis lab data.
- Listing of patients with laboratory abnormalities of CTC grade 3 or 4 by treatment with values flagged to show the corresponding CTC grades and the classifications relative to the laboratory reference ranges by treatment. This listing will be provided for hematology, biochemistry and urinalysis lab data combined.
- A listing of patients with grade $\frac{3}{4}$ CK elevation with values flagged to show the corresponding CTC grades and the classifications relative to the laboratory reference ranges by treatment.
- Listing of pregnancy test results by treatment

3.8.3 Vital signs

Vital sign assessments are performed in order to characterize basic body function. The parameters collected in this study are: weight (kg or lb), height (cm or inches), body temperature (°C), heart rate (beats per minute), systolic and diastolic blood pressure (mmHg).

The criteria for clinically notable abnormalities are depicted in [Table 3-2](#) and [Table 3-3](#).

Table 3-2 Clinically notable elevated values

Variable	Criteria
Systolic BP	≥ 150 mmHg and an increase ≥ 20 mmHg from baseline
Diastolic BP	≥ 90 mmHg and an increase ≥ 20 mmHg from baseline
Body temperature	$\geq 38^{\circ}\text{C}$
Weight	increase from baseline of $\geq 10\%$
Heart rate	≥ 100 bpm with increase from baseline of ≥ 20 bpm

Table 3-3 Clinically notable below normal values

Variable	Criteria
Systolic BP	≤ 90 mmHg and a decrease ≥ 20 mmHg from baseline
Diastolic BP	≤ 50 mmHg and a decrease ≥ 15 mmHg from baseline
Body temperature	$\leq 35^{\circ}\text{C}$

Weight decrease from baseline of $\geq 10\%$

Heart rate ≤ 50 bpm with decrease from baseline of ≥ 15 bpm

The following summary will be produced for heart rate, diastolic BP and systolic BP, body temperature and weight change by study phase, dose cohort and overall:

- Number and percentage of patients with at least one post-baseline vital sign abnormality (in both directions, i.e. both elevated and below normal values)

The following listing will be produced by study treatment and overall:

- Patients with clinically notable vital sign abnormalities
- All vital sign assessments will be listed by patient and vital sign parameter

In both listings, the clinically notable values will be flagged and also the assessments collected later than 30 days after the last treatment/exposure date will be flagged.

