In Phase III myelofibrosis clinical studies, grade 3 or 4 herpes zoster infection was reported in one patient.

Tuberculosis

In Phase III myelofibrosis studies, tuberculosis of any grade was reported in 1.0 % of patients. Potential confounding factors include exposure to corticosteroids and history of hematological malignancies, diabetes, emphysema, BMI below 20 kg/m², asthma, bronchitis, and smoking as risk factors in the general population. Relation to INC424 is not clear due to the low number of cases and potential confounding factors involved.

Increased systolic blood pressure

In the phase III pivotal clinical studies an increase in systolic blood pressure of 20 mmHg or more from baseline was recorded in 31.5% of patients on at least one visit compared with 19.5% of the control-treated patients. Relation to INC424 is not clear at this point.

PML (progressive multifocal leukoencephalopathy)

One case of PML has been reported in a myelofibrosis patient receiving INC424. It would be important to note that an atypical feature of this disease occurred quickly (approximately one month) after initiation of INC424 treatment. Infections are well known complications in myelofibrosis patients. PML has been reported in myeloproliferative disease patients who are not taking INC424.

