10.5.1.3 Other safety data

Summary statistics for data from other tests will be provided, notable values will be flagged, and any other information collected will be listed as appropriate by study phase. Descriptive summary statistics will be provided for electrocardiogram (ECG) and vital sign data, as follows:

- ECG: Changes from baseline to end of study, and new or worsening abnormalities.
- Vital signs: Summary statistics of raw data and change from baseline values (means, medians, standard deviations) plus newly occurring or worsening abnormalities.

Listings with flagged notable values and any other information collected will be provided as appropriate.

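### SAP 3.8.3 omits the raw-value and change-from-baseline vital-sign summaries that protocol 10.5.1.3 requires, and its one table leaves systolic rises of 20 mmHg or more that stay below 150 mmHg to the patient listings

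*SAP*

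**What the plan says.** Protocol 10.5.1.3 (Other safety data) plans: "Vital signs: Summary statistics of raw data and change from baseline values (means, medians, standard deviations) plus newly occurring or worsening abnormalities". That is three outputs: raw values, change from baseline, and abnormalities.

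SAP 3.8.3 (Vital signs) names a single summary, "Number and percentage of patients with at least one post-baseline vital sign abnormality", in both directions, and two listings. One listing covers patients with notable values. The other is complete: "All vital sign assessments will be listed by patient and vital sign parameter". A systolic value is notably elevated if it is "≥ 150 mmHg and an increase ≥ 20 mmHg from baseline", so both conditions must be met. No table of raw values or of change from baseline is named.

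The INC424 background in protocol 1.4.2.2.1 describes the phase III observation without an absolute floor, as "an increase in systolic blood pressure of 20 mmHg or more from baseline". The rates it gives, counting any visit, are 31.5% for INC424 and 19.5% for control. It adds that the relation to INC424 is not clear.

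**The concern.** A programmer who follows SAP 3.8.3 produces one of the three outputs that the protocol promises. Means, medians and standard deviations of blood pressure over time, and of its change, would not be in the report's tables.

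The table that remains cannot fill the gap for systolic pressure, because it counts a rise only when the value also reaches 150 mmHg. Increased systolic pressure is one of the topics that the protocol introduces under INC424 side effects, and there it is described as a change from baseline. Both the average shift and the proportion with a rise of that size would have to be worked out by hand from listings.

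Other outputs do not clearly supply it. Under protocol 8.1.1 an abnormal test result becomes an adverse event only if it causes signs or symptoms, is judged clinically significant, or leads to therapy or a change in study drug. An asymptomatic rise need not qualify. No blood-pressure term is among the adverse events of special interest in SAP 3.8.1.5.

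**Working it through.** **1. Outputs side by side**

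| Output | Protocol 10.5.1.3 | SAP 3.8.3 |
|---|---|---|
| Summary of raw values | yes | not named |
| Summary of change from baseline | yes | not named |
| Abnormalities | new or worsening | n (%) with a notable value |
| Listings | yes, notable values flagged | yes, notable values flagged |

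The general rule in SAP 3.1 says that continuous data get descriptive statistics, but it does not mention change from baseline. Where the SAP wants change from baseline it says so: spleen length (3.7.2), ECG (3.8.4.1), patient-reported outcomes (3.9.1.1, 3.9.2, 3.9.4).

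**2. Who can be missed**

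Baseline = value − rise. If the rise is at least 20 and the value is below 150, then baseline < 150 − 20 = 130 mmHg. So every patient with baseline of 130 mmHg or more and a rise of 20 mmHg or more is counted, and only those who start below 130 can be missed. Example: 118 to 146 mmHg is a rise of 28 and is not counted.

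**3. The background rates**

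Using the arm sizes in protocol Table 1-6, INC424 is 155 + 144 = 299 and control is 154 + 72 = 226. Then 44/226 = 19.5%, which matches. For INC424, 94/299 = 31.4% and 95/299 = 31.8%, so 31.5% is close but not exact. The counts and denominators behind the two rates are not given.

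**4. Share missed (simulation)**

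From the documents: 31.5% with any rise of 20 mmHg or more, used only for calibration, and 50 treated patients (30 in Phase Ib and 20 in Stage 1, Amendment 2 rationale). Assumed, because the documents do not give them: baseline mean 115 to 140 mmHg, baseline SD 12 to 18, mean shift on treatment 0 to 6 mmHg, 12 post-baseline visits.

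Model: observed baseline = usual level + visit error; each later value = usual level + shift + visit error. The visit-error SD is solved so that P(any rise ≥ 20) = 0.315, which gives 9.2, 7.8 and 6.4 mmHg for shifts of 0, 3 and 6. Share missed = 1 − P(rise ≥ 20 and value ≥ 150 at the same visit) / 0.315. Without the floor, 0.315 × 50 = 15.8 patients would be counted.

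| Assumed mean baseline | Share missed | Counted of 50 with the floor |
|---|---|---|
| 115 | 83–96% | 0.6–2.6 |
| 120 | 75–90% | 1.6–3.9 |
| 125 | 65–78% | 3.5–5.5 |
| 130 | 54–59% | 6.4–7.3 |
| 135 | 37–43% | 8.9–9.9 |
| 140 | 19–31% | 10.8–12.7 |

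The same model run at a mean of 145 mmHg gives 8–21% missed.

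**5. Dependence on follow-up**

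Protocol Table 7-1 schedules vital signs at Week 13 and every 4 weeks to Week 105: (105 − 13)/4 + 1 = 24 visits, before counting the earlier ones. Take the no-shift model, calibrated to 31.5%, and extend it to 26 visits with no drug effect. The any-visit rate, without the floor, becomes 43% if calibrated at 12 visits and 55% if calibrated at 6.

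**The case against.** The strongest reply is that this is a tabulation gap and not lost data. Every vital-sign value is listed by patient, so in about 50 patients the count can be recovered. Clinically significant or treated rises enter the adverse-event tables. Both documents base safety mainly on adverse events and laboratory values, and no decision rule uses the vital-sign table. All of this stands, and it limits the weight of the point.

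It can also be said that SAP 3.1 applies to continuous data in general (body weight is one of its examples) and that the SAP leaves some output detail to a companion document, RAP M7, which is not available here. This stands only in part. SAP 3.1 does not mention change from baseline, SAP 3.8.3 does not refer to RAP M7, and 3.8.3 states which summary will be produced.

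A reader might infer three stronger things that the documents do not support:

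- **That the 150 mmHg floor contradicts the protocol.** The protocol sets no threshold for a vital-sign abnormality. The 20 mmHg figure is background from earlier studies, and the SAP combines an absolute value with a change for diastolic pressure and heart rate as well.
- **That a known harm is being hidden.** The protocol says the relation to INC424 is unclear, and the values stay in the listings.
- **That the reported figure would fall below the 19.5% control rate.** This depends on the assumed baseline. At a mean of 140 mmHg the table would show 10.8/50 to 12.7/50, or 21.6% to 25.4%.

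**Conclusion.** The discrepancy holds on the text alone: SAP 3.8.3 leaves out, without a stated reason, two summaries that protocol 10.5.1.3 requires. It also follows by arithmetic that systolic rises of 20 mmHg or more in patients starting below 130 mmHg can be absent from every vital-sign summary.

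How many are absent cannot be fixed from the documents. The range of 19% to 96% rests on assumed baseline means of 115 to 140 mmHg and on calibration to the phase III rate. More than half are missed at means of 130 or below, under half at 135 or above, and fewer still at 145.

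A direct comparison with 31.5% and 19.5% is not supported even without the floor. The trial has no control arm, and the longer visit schedule alone could raise an any-visit rate to 43–55% with no drug effect. The point is a modest correction to safety reporting and does not affect the efficacy conclusions.

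**What to change.** In SAP 3.8.3:

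- Restore by-visit summaries of raw values and change from baseline (mean, median, SD) for each vital sign, or state why the protocol's plan is not followed.
- Beside the notable-value table, add a descriptive row giving the number and percentage of patients with a systolic rise of 20 mmHg or more from baseline at any on-treatment visit, with no absolute floor. Keep the existing criteria as they are.
- Limit that row to a fixed window, such as the first 24 weeks, or state the number of visits behind it. Add a note that it is not to be compared directly with the phase III rates.

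The cost is SAP wording and a few extra tables from data already collected. Only tabulation changes; clinical management does not.
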